7.0 Risks

- Following a special diet and keeping a record of what is eaten and medication use may be inconvenient to participant.
- The participant will be required not to eat or drink, except water, after 10 pm on the night before testing visits at the end of study weeks 1 and 9. This may cause the participant to have a headache or a feeling of weakness, or the participant may become irritable.
- Blood draw: Blood draws can cause redness, soreness, bleeding or bruising at the needle stick site. The CRC nurses will be careful and use sterile technique. Sometimes people feel faint. The nurse may put some cream (called EMLA) on the skin to numb the area so the participant will not feel the needle stick as much. The numbing cream may make the skin change color, but this is rare.
- DEXA: Because DEXA is an x-ray, the participants are exposed to some radiation. The amount of radiation from the 2 DEXA scans is equal to the amount of radiation in the natural environment if the participants were to walk around outside for 17 days.
- Because the participant will not be taking medication for GERD while are participating in this study, it is possible that GERD symptoms may get worse.
- 24-hour pH Monitoring:
 - Lidocaine: Lidocaine, a numbing drug, has an awful taste and causes a strange feeling in the mouth. There is a rare side effect that this drug may cause hoarseness and loss of voice. There is a very rare risk that this drug may cause problems with heart rhythm.
 - Possible risks for the participants during 24-hour study include: nasal discomfort, injury to nasal passages such as nose bleedings, allergic reaction to lidocaine gel used to numb the nasal passages for placement of tube, and rupture of the esophagus by the long tube which may require an operation.
 - Smart Pill: You may experience discomfort when swallowing the smart pill. In rare cases, the smart pill could get lodged or stuck in your esophagus. This may require a procedure to remove the pill. If you have an abnormality in how your esophagus works this may increase the risk.

•

Risks that are not known:

There are no known risks with any of the 4 diets. If new information is discovered that may affect the risks or benefits of this study, the participant will be told so that he/she can decide whether or not to remain in the study.

8.0 Reporting of Adverse Events or Unanticipated Problems involving Risk to Participants or Others

All serious and unanticipated adverse events or problems involving risks to subjects that may possibly be or are known to be related to the research activity will be reported promptly to the IRB office per Vanderbilt University IRB Policy. The PI will ensure proper data and safety monitoring for the materials and data used for the purposes of this study.

9.0 Study Withdrawal/Discontinuation

Subjects may choose not to participate in this research study. This decision will not alter the routine care administered by the physician or the risks associated with standard of care procedures. Additionally, the participant will be removed from this study if the investigator does not think it is in best interest for the subject to be in this study. If the participant is removed from the study he/she will be told the reason why.

10.0 Statistical Considerations

Data Analysis: To determine *if percent time with pH < 4 differs by diet treatment group*, we will use multivariable linear regression modeling. Models will include baseline percent time pH < 4.0 and other variables key to disease severity to improve model precision and the diet treatment groups as indicator variables. We will determine *if the primary outcome (% time pH < 4.0) differs by intervention arm*. We will use a linear mixed effects regression model to determine if percent time < pH 4 (Y_{ij}) differs by diet group. The model will incorporate the proportion of time each subject is observed so that subjects that drop out 2 or fewer weeks early are included in the analysis and allowed to have a smaller response to the diet intervention. In particular, for subject i at time j , $Y_{ij} = \bar{Y} + b_i + \bar{X}_{1i} * t_{ij} + \bar{X}_{2i} * t_{ij} + \bar{X}_{3i} * t_{ij} + \bar{X}_{4i} * t_{ij} + e_{ij}$ where $b_i \sim N(0, \sigma^2_b)$ is a subject specific random intercept used to account for repeated observations on the same subject, \bar{Y} is the mean at baseline, X_{pi} are indicator variables for diet group assignment with corresponding effects at 9 weeks \bar{X}_p ($p=1,..,4$), and independent errors $e_{ij} \sim N(0, \sigma^2_e)$. The time the outcome is measured, t_{ij} , is included in the model such that $t_{i1} = 0$ at baseline, $t_{i2} = 1$ for subjects who complete the entire study, and $t_{i2} = p$ for subjects who leave after completing a proportion p of the weeks and come back for final pH testing. Subjects will be included if $p \geq 0.8$.

It is understood that some subjects may drop-out, and thus, not return for the final follow-up visit at week 9, in which case we would have missing values for some response variables. Frequently such dropouts are not a random sample of the entire cohort, and

analysis of only the complete cases would bias the results. *We will now request to subjects that inform of us they are dropping out between weeks 7 to 9 that they come in for a final visit. We have found that about 2/3 of subjects will agree to come in for a final visit even if they are not continuing to the end of study (week 9). This will significantly reduce the potential for missing data.* We will also attempt to obtain the specific reason for dropout on a case by case basis. Indirect information about the nonrandom dropouts will be obtained by using binary logistic models to predict the probability of dropping out using baseline variables. Thus, the impact of dropout on our results will be compared using assumptions that vary from missing completely at random to informative missing.

Sensitivity Analyses: We will use the daily diet data and daily medication checklist (type and amount) to conduct secondary analyses and verify the assumptions of our primary model. Summary statistics by diet group will be calculated to determine if weight loss, PPI use, total CHO, and simple CHO are consistent with the study design. We will also use the linear mixed effects model to determine if total and simple CHO are associated with total percent time < pH 4 by replacing the indicator variables in the primary model with these continuous covariates and their interaction. A secondary analysis of changes in PPI use over time will be considered. For this analysis, we will use the diary card data to create continuous variables of the weekly dose of PPI. PPI dose will be the outcome in a linear mixed effects regression model that includes time modeled flexibly using restricted and diet group indicators. An analogous model using weight as the outcome will be estimated. Our study is designed for subjects to maintain weight, but if weight loss differs by treatment arm, it may introduce confounding into our study. We will include weight loss as a covariate in our regression model to determine if our results are altered compared to the main analysis. This additional sensitivity analyses will be conducted as needed, for example where weight change is significantly different among groups, to assure effects are due to dietary not body weight change.

Interpretation: Given our expertise in nutrition, metabolism and obesity ([name] and [name]), GERD ([name] and [name]), and GERD biostatistics ([name]), our group is ideally suited for executing and interpreting this study. We predict that we will uncover key diet related factors driving GERD symptoms and esophageal acid exposure in the obese Veteran, and we will develop a predictive risk model based on sound science. Physiologically, the proposed study will determine whether changes in several plausible gut hormones and/or improvement in insulin sensitivity is associated with the improvement in GERD with the dietary intervention.

Our preliminary data suggest that reduction of simple carbohydrate was most robustly associated with GERD resolution. The current study design will more rigorously address whether it is simple or total carbohydrate that is the driver of GERD symptoms and reflux. This has important implications for the development of more broadly disseminated dietary recommendations; a moderately high carbohydrate but low simple carbohydrate diet may be more tolerable to certain individuals than a low total carbohydrate approach. Conversely, if total carbohydrate is determined to be the major factor in the response, we will by definition be suggesting fairly high-fat and high-protein dietary intakes. Such approaches are increasingly recognized to have efficacy for weight loss as well as improvement in cardiometabolic parameters such as lipid profiles. Although dietary fat intake has been positively associated with GERD in obese subjects,⁵² the 4-5 investigations comparing effects of high fat to low fat diets on esophageal acid exposure and GERD symptoms have shown no worse outcomes with high fat diets.²⁰⁻²³ Certainly in metabolically at risk populations (such as obese Veterans) we would be conscientious

regarding the source and composition of dietary fat intake, as well as the protein load of the diet.

The next level of analysis, for example, if lowering simple CHO intake reduces symptoms or esophageal acid exposure, will determine whether it is related to total dietary fiber intake or glycemic load. This analysis will reveal the extent to which “processing” of food ingredients contributes to GERD symptoms. The finding that higher dietary fiber and/or lower glycemic load is associated with less GERD would suggest that somewhat less of a focus on macronutrient composition (i.e., CHO vs fat) may be warranted, with more of a focus on consuming foods closer to their natural state.

Finally, by profiling several relevant gut hormones and assessing insulin sensitivity, we will investigate relationships for factors involved in plausible biological hypotheses for the effects of dietary carbohydrate on GERD symptoms. Our observation that reduction in simple CHO intake improves insulin sensitivity is consistent with a nutrient excess mechanism for insulin resistance. The mechanistic link between insulin sensitivity and GERD is most often considered in the context of weight loss, reduced waist circumference and improvement in abdominal pressures, and GERD symptoms. Here we investigate relationships that may suggest that improving insulin sensitivity independent of weight loss improves GERD. This has important implications for clinical translation, as induction of significant weight loss, and especially, long term maintenance of weight loss is a major clinical challenge. To reap clinical benefits on GERD and GERD symptoms without the requirement for weight loss would be a major clinical advantage. While gastrin release is not clearly understood to be differentially regulated by different macronutrients, GLP-1 and other gut hormones may well be. Thus, we will determine whether changes in the levels of any of the proposed gut hormones correlate with improvement in GERD. Identification of such an effect will drive specific hypotheses for future studies to uncover the mechanisms and clarify a mechanistic role in GERD response.

Thus, analysis of the data from the proposed study will determine which factor(s), fiber or glycemic load, total or simple carbohydrate, lower or higher fat in the context of more or less simple sugar, or gut hormones, should be targeted in next phase larger scale intervention studies. These findings will also drive the development of future experiments designed to understand the mechanistic effects of the optimal diet for GERD.

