- HTLS Diet: 55% total CHO (85% complex / 15% simple CHO), 30% fat, 15% protein
- LTHS Diet: 35% total CHO (½ complex / ½ simple CHO), 50% fat, 15% protein
- LTLS Diet: 35% total CHO (85% complex / 15% simple CHO), 50% fat, 15% protein

Power Analysis and Sample Size: Our primary outcome is a continuous variable, percent time pH < 4.0 in the 24hr period. This is based on the clinical gold standard of pH < 4.0 for > 5.5% of the 24hr period. To determine sample size, we used data from 205 obese patients with chronic GERD from [name] clinic population. In this sample, the SD for percent time < pH was 9.8 and the interclass correlation was 0.39 ($\omega = \omega^2_b / (\omega^2_b + \omega^2_e)$). We used these values as inputs into a statistical simulation (10,000 replications) to determine the probability of detecting any treatment group effect using the linear mixed effects model. The following table presents the power of an overall (4 d.f.) test to detect various absolute changes in pH by diet groups ($\omega_1, \omega_2, \omega_3, \omega_4$). We assume $n_1=40$ subjects per group complete the entire study and $n_2=5$ or $n_2=3$ subjects per group complete 80% of the study before returning for pH testing. We use a two-sided significance level of 0.05.

Absolute effect size	3.7%, 3.7%, 3.7%, 3.7%	0%, 4.5%, 4.5%, 4.5%	0%, 4%, 4%, 4%	0%, 0%, 5%, 5%	0%, 0%, 0%, 7%
Power ($n_1=40, n_2=5$)	0.80	0.89	0.80	0.85	0.87
Power ($n_1=40, n_2=3$)	0.79	0.88	0.79	0.83	0.86

Power for different effect size scenarios that give 80%-90% power are presented in the table. If the absolute change in percent time pH < 4 for each of the four diet groups is 3.7%, we will have 80% power to detect any effect of diet. If 1 diet group is not effective and the other groups have a 4.5% effect, we have almost 90% power to detect a diet effect. In our pilot data, the 25th/50th/75th percentiles of percent time pH < 4 were 4.8%/8.5%/12.4%. Thus, a 3.7% decrease is a change from the median to 25th percentile, a 4% decrease is a change from the 75th percentile to the median, a 5% decrease is a change from the 80th percentile to the median, and a 7.6% decrease is a change from the 75th to the 25th percentile. The standard error for any pairwise comparison between groups will be 1.9% under all scenarios ($n_1=40$ and $n_2=3$ or $n_2=5$).

2.3 SPECIFIC AIMS:

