We recently conducted a nutrition intervention utilizing a low carbohydrate / high fat diet in 144 Caucasian and African American adults age 21-50 years with Class I obesity (BMI 30.0-39.9). At baseline, 25% of subjects reported experiencing GERD symptoms (heartburn, reflux and/or indigestion) at least once a week. Over 1/3 used a proton pump inhibitor (PPI) or histamine 2 receptor antagonist (H₂RA) at least once a week. At baseline, we found that subjects with GERD had significantly higher total sugar intakes (101.6 ± 50.3 vs 82.5 ± 40.9 grams/day, $p = 0.024$), but not higher total fat intakes. Notably, total sugar intake was a strong predictor of having GERD symptoms ($p = 0.007$). *Most unexpectedly, all GERD symptoms and medication use had resolved by completion of the 9-week low carbohydrate / high fat diet intervention.* Moreover, reduced total sugar intake was significantly associated with improved insulin sensitivity (HOMA-IR score: $r = 0.37$, $p = 0.001$), independent of weight loss.

Overarching Hypothesis: Our overarching hypothesis is that the type (not just the amount) of dietary carbohydrate intake contributes to GERD symptoms in obese persons.

Specific Hypothesis: Our preliminary findings suggest a physiological mechanism between dietary intake and GERD that may be related to type of dietary carbohydrate intake (complex vs simple carbohydrate). We hypothesize that modifying the type of dietary carbohydrate consumed - by reducing the proportion of simple carbohydrate (sugars) consumed - will reduce or resolve GERD symptoms and medication use in obese veterans with chronic GERD. We further hypothesize that the mechanistic effects of reducing simple carbohydrate intake is related to either: a) improved dietary fiber intake and/or glycemic load, and thus, reduced amount and duration of esophageal acid exposure; and/or b) improved insulin sensitivity which would positively influence the function of key gastrointestinal hormones (ie, gastrin, glucagon, GLP-1, ghrelin¹¹) that regulate gastric motility and/or lower esophageal sphincter function.

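### No primary contrast isolates carbohydrate type or amount; the overall 4-d.f. test can be significant with no type effect and with no difference between arms

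*Combined protocol and SAP*

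**What the plan says.** The overarching hypothesis in Section 2.3 is that "the type (not just the amount) of dietary carbohydrate intake contributes to GERD symptoms in obese persons". The Interpretation part of Section 10.0 says the design will address "whether it is simple or total carbohydrate that is the driver of GERD symptoms and reflux". The General Approach in Section 2.0 and Aim 1 are broader and cover amount as well as type.

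Section 2.2 defines four diets: 55% or 35% of energy from carbohydrate, crossed with half or 15% of that carbohydrate as simple sugars. Within each amount level the targets for total carbohydrate, fat and protein are the same. Between amount levels, fat moves from 30% to 50%.

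The primary analysis in Section 10.0 is a mixed model with a common baseline mean, a random subject intercept and one diet effect per arm. It is used to determine "if the primary outcome (% time pH < 4.0) differs by intervention arm". The power analysis in Section 2.2 names the test: it tabulates the "power of an overall (4 d.f.) test to detect various absolute changes in pH by diet groups".

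Sections 2.1 and 10.0 (Sensitivity Analyses) add a secondary model in which continuous total and simple carbohydrate intake, with their interaction, replace the arm indicators. No contrast between the randomised low-simple and high-simple arms is specified, and none for amount.

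**The concern.** A factorial layout lets the randomised comparison answer whether type matters, whether amount matters, and whether one depends on the other. A single overall test answers none of these. Two problems follow.

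First, an effect of amount alone (or of the fat that replaces carbohydrate) makes the overall test significant. The primary result could then be read as support for a hypothesis about type on which it is silent.

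Second, the model has one effect for each of the four arms, control included, each measured from the common baseline mean. The 4-d.f. null is therefore no change in any arm. A change shared equally by all four arms, which says nothing about the diets relative to each other, is enough to reject. Such a shared change is not far-fetched: Section 4.0 admits only subjects whose baseline acid exposure is high. How far that matters depends on whether the qualifying test is also the model's baseline, which the documents leave unclear.

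In either case the choice between type and amount, which is what the trial says it will settle, would rest on comparisons chosen after the fact or on the secondary intake model.

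**Working it through.** **Inputs.** From Section 2.2: "We use a two-sided significance level of 0.05"; "the SD for percent time < pH was 9.8"; "the interclass correlation was 0.39"; "We assume $n_1=40$ subjects per group complete the entire study and $n_2=5$ or $n_2=3$ subjects per group", with the second group measured at t = 0.8. From Section 10.0: the model described above. The documents do not say whether 9.8 is the residual or the total SD, so both readings are shown. Effects are listed in the protocol's order HTHS, HTLS, LTHS, LTLS. The power table does not name its positions, so this ordering is an assumption.

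**Step 1, variances.** Residual reading: residual variance 9.8² = 96.04; between-subject variance 96.04 × 0.39/0.61 = 61.40. Total reading: 96.04 × 0.61 = 58.58 and 96.04 × 0.39 = 37.46.

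**Step 2, formulas.** Generalised least squares for this model with 40 + 5 per arm gives each diet effect variance v and each pair covariance c: v = 3.427, c = 0.337 (residual reading) or 2.091, 0.206 (total reading). For arm effects b with mean m:

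- 4 d.f.: λ = Σ(b − m)²/(v − c) + 4m²/(v + 3c)
- 3-d.f. between-arm: λ = Σ(b − m)²/(v − c)
- type contrast, the average of (HTLS − HTHS) and (LTLS − LTHS): SE = √(v − c), λ = (contrast/SE)²

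Power is the probability that a noncentral chi-square exceeds 9.488, 7.815 or 3.841. In the residual reading v − c = 3.090 and v + 3c = 4.438.

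**Step 3, reproduce the plan's table** (4 d.f.).

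| Effects | Stated, n2=5 | Residual reading | Total reading | Stated, n2=3 | Residual reading |
|---|---|---|---|---|---|
| 3.7 in all four | 0.80 | 0.815 | 0.966 | 0.79 | 0.801 |
| 0, 4.5, 4.5, 4.5 | 0.89 | 0.895 | 0.989 | 0.88 | 0.885 |
| 0, 4, 4, 4 | 0.80 | 0.802 | 0.961 | 0.79 | 0.788 |
| 0, 0, 5, 5 | 0.85 | 0.859 | 0.980 | 0.83 | 0.847 |
| 0, 0, 0, 7 | 0.87 | 0.883 | 0.986 | 0.86 | 0.872 |

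The residual reading reproduces all ten entries within 2 points; the total reading reproduces none. This also confirms that the tabulated test is the one whose null is zero change in every arm. The stated pairwise SE of 1.9 goes the other way: √(2 × 3.090) = 2.49 in the residual reading, 1.94 in the total reading. The plan's own figures therefore do not share one variance. The residual reading is the base case below, and the total reading follows in brackets.

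**Step 4, rejection with no type effect** (n2 = 5).

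- Amount only (0, 0, 5, 5): m = 2.5, Σ(b − m)² = 25. λ = 25/3.090 + 4 × 6.25/4.438 = 8.09 + 5.63 = 13.72; the 4-d.f. test rejects with probability 0.859 [0.980]. A 3-d.f. test has λ = 8.09 and rejects with probability 0.660 [0.878]. The type contrast is zero and rejects at 0.05.
- 3.7 points in every arm: λ = 4 × 13.69/4.438 = 12.34; the 4-d.f. test rejects with probability 0.815 [0.966]. The 3-d.f. test and the type contrast reject at 0.05.

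**Step 5, a 5-point type effect** (0, 5, 0, 5). The 4-d.f. λ is again 13.72, so that test responds identically to a pure type and a pure amount effect. Type contrast: SE = √3.090 = 1.76 [1.37], λ = 25/3.090 = 8.09.

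| Test | Residual reading | Total reading |
|---|---|---|
| Overall, 4 d.f. | 0.86 | 0.98 |
| Between-arm, 3 d.f. | 0.66 | 0.88 |
| Type contrast, 1 d.f. | 0.81 | 0.95 |

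A 2,000-replicate simulation of the residual reading gave 0.846, 0.640 and 0.802.

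**Step 6, where the type contrast does badly** (residual reading).

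- (0, 0, 0, 7): contrast 3.5, λ = 12.25/3.090 = 3.96, power 0.51 against 0.88 for 4 d.f.
- (0, 4.5, 4.5, 4.5): contrast 2.25, λ = 5.06/3.090 = 1.64, power 0.25 against 0.90 (0.895) for 4 d.f.

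**The case against.** The strongest defence has four parts.

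- **The protocol does plan to separate type from amount**, through the continuous-intake model. That is true and must be acknowledged. But the model is secondary and rests on recorded intake, which is not protected by randomisation; Section 6.0 itself notes underreporting in people with high BMI. It does not replace a randomised contrast.
- **The trial is not only about type.** The and/or framing in Section 2.0 and Aim 1 support this, and the hypotheses in Section 2.3 speak of symptoms and medication use rather than pH. This stands: type should not be imposed as the only primary question. It supports naming both factors, which one overall test cannot separate.
- **The wording of Section 10.0 on its own could mean a 3-d.f. between-arm test.** On that reading the equal-change problem disappears, but a pure amount effect still gives significance in 66% to 88% of trials.
- **The overall test is robust to where the effect lies.** This stands too; Step 6 shows the cost.

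A reader might infer that the plan throws away about 15 points of power. The documents do not support that. The gap (0.81 against 0.66) is against a 3-d.f. test, not the 4-d.f. test that the protocol powers, and it shrinks to about 8 points with 9.8 as total SD. Against the documented test the type contrast has about 5 points less power (0.81 against 0.86), because the 4-d.f. test also counts change common to all arms. A reader might also infer that the trial would fall back on pairwise tests. Section 2.2 gives a pairwise standard error, but no pairwise test is planned.

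**Conclusion.** The point holds as a matter of interpretation, not of lost power. No planned primary contrast isolates type or amount. At 40 + 5 per arm, the documented test rejects in 86% of trials under a 5-point pure amount effect and in just over 81% under an equal 3.7-point change in all arms (98% and 97% with 9.8 as total SD). In both cases a type contrast would reject only at its 5% level.

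These figures rest on the Section 10.0 model, an ICC of 0.39, the ordering of the arms stated above, and the large-sample chi-square approximation. The qualitative conclusion does not depend on which SD reading is right. The change is advisable because it determines what a positive result would mean.

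**What to change.** In Section 10.0, prespecify from the same model, for percent time pH < 4:

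1. the type contrast, the average of (HTLS − HTHS) and (LTLS − LTHS);
2. the amount contrast, the average of (LTHS − HTHS) and (LTLS − HTLS), noting that fat changes with amount;
3. multiplicity control across the two: either a fixed order with type first, or split alpha;
4. the amount-by-type interaction and the two within-pair type effects, reported whatever the result;
5. any overall test as supportive only, and as a 3-d.f. between-arm test.

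In Section 2.2, state the power of both contrasts, say whether 9.8 is the residual or the total SD, and reconcile the 1.9 standard error with the power table.

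The cost is wording: data, model and sample size are unchanged. The statistical price is the lower power in Step 6 when the effect sits in one arm or is equal in the three non-control arms. Splitting alpha equally would lower type-contrast power at 5 points from 0.81 to 0.73 (5/1.758 = 2.844; 2.844 − 2.241 = 0.603), or from 0.95 to 0.92 in the total reading. The interaction will be imprecise: its SE is √(4 × 3.090) = 3.52 points in the residual reading. It should be reported as an estimate with its interval rather than used as a gate.

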Background PPI Use: Acid suppression therapy is commonly prescribed, particularly in the VA for symptomatic GERD relief. Our research team, which includes practicing clinicians and experienced GERD researchers (Drs. [name] and [name]) debated a design wherein we would require research subjects to discontinue all acid suppression therapy for the duration of the study. It is clear that based upon symptom burden and for the purposes of adherence to study procedure that this would not be feasible. Further, we were concerned that if acid related damage were occurring off of acid suppression, then such a design may not be ethical. Thus, we have adapted a much more "clinical" or "intention-to-treat" mindset to the study design. Indeed, in a clinical setting, patients are most often treated empirically. Thus, we will follow AGA guidelines⁹ and have subjects maintain acid suppression therapy during the intervention, with the exception of the 7-day period prior to impedance and manometry testing. To determine the effect of acid suppression on the hormonal milieu we will now draw blood pre and post medication discontinuation. The only potential confounder to this approach would be if the efficacy of the dietary intervention were dependent upon having a highly acid and refluxing esophageal environment. This does not seem biologically plausible, and additionally the efficacy of the dietary intervention to reduce GERD in our preliminary data was not acid dependent given that all subjects self-discontinued use of acid suppression medications. *We will perform secondary analysis in which changes in PPI use over time will be assessed. We will use the daily medication (type and dose) and diet checklist data and 24hr diet recall data to conduct secondary analyses and verify the assumptions of our primary model. Summary statistics by diet group will be calculated to determine if weight loss, PPI use, total CHO, and simple CHO are consistent with the study design. We will also use the linear mixed effects model to determine if total and simple CHO are associated with total percent time pH < 4 by replacing the indicator variables in the primary model with these continuous covariates and their interaction. A secondary analysis of changes in PPI use over time will be considered. For this analysis, we will use the daily medication checklist (type, amount and dose) to create continuous variables of the weekly dose of PPI. PPI dose will be the outcome in a linear mixed effects regression model that includes time modeled flexibly using restricted and diet group indicators. An analogous model using weight as the outcome will be estimated.*

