6.0 Study Procedures

Randomization: 200 subjects (50 per arm) will be randomized to diet treatment arm. we have reviewed drop-out rate from clinical trials in gastroenterology in this population ([name] and [name] personal communications), which would predict a 20% drop out rate. The number of subjects to enroll reflects a completion rate of 80% (enroll 50 per arm = 200 subjects x 0.80 = 160 completers). In considering that drop out could be higher, we will now include subjects in our final analyses who notify us they are dropping-out between weeks 7-9 by asking them to return for a final visit at the time of drop-out (we do this regularly and get agreement from about 66% of subjects to return for a final testing session even if they are not continuing to wk 9). Randomization of subjects will be carried out using unified reproducible methods (i.e. saved random number seed) provided by the Biostatistician ([name]). We will use a permuted block randomization scheme, stratifying on gender to ensure this covariate is balanced

between randomization groups. The block size will be varied randomly. Treatment assignments will be contained in sealed, thick envelopes to be opened after informed consent is obtained.

Overall Schema:

Timepoint	Baseline	Day 1-7	End Wk 1	Day 8-57	Day 57-63	End Wk 9
Consent & Enrollment	X					
Randomization			X			
Bloodwork	X		X		X	X
Diet Intervention						
Off PPIs #1						
Clinical Testing #1				X		
Off PPIs #2						
Clinical Testing #2						X

Testing Procedures:

Baseline levels of all measures listed below will be obtained prior to study day 1.

PPIs will be stopped for 1 week, medications that affect gastric motility for 2 days, H₂RAs for 2 days, and antacids for 2 days - *prior to testing on study days 7 and 63. Additional blood work will be drawn on study day 57 for evaluation of levels prior to discontinuation of PPIs #2.*

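### The p ≥ 0.8 inclusion rule shuts out a subject who leaves two weeks early (7/9 = 0.778), whom the same paragraph and Section 6.0 include

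*Combined protocol and SAP*

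**What the plan says.** Three statements bear on who enters the primary analysis.

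- **Section 10.0, Data Analysis, in words.** The model scales the diet effect by time on study, with this stated purpose: "so that subjects that drop out 2 or fewer weeks early are included in the analysis and allowed to have a smaller response".
- **Section 10.0, Data Analysis, in numbers.** The second time value equals p for early leavers, described as those "who leave after completing a proportion p of the weeks and come back for final pH testing. Subjects will be included if"; the condition that follows is p ≥ 0.8. The same sentence introduces t as "The time the outcome is measured".
- **Section 6.0, Randomization.** "we will now include subjects in our final analyses who notify us they are dropping-out between weeks 7-9", and this is to be done "by asking them to return for a final visit at the time of drop-out".

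The missing-data text in Section 10.0 supports these but is narrower. It asks subjects who report that "they are dropping out between weeks 7 to 9 that they come in for a final visit", in order to reduce missing data. It does not itself say that they enter the analysis.

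The intervention lasts 9 weeks (Section 2.1, Duration of Intervention; Section 2.3, Aim 1). Meal plans are taught at the end of study week 1 (Section 2.2, Diets), and the Section 6.0 schema places randomization there too. The Power Analysis in Section 2.2 models early leavers as completing 80% of the study.

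**The concern.** The verbal rule and the numeric rule sit in the same paragraph and give different answers for a subject who leaves exactly two weeks early. Section 6.0 sides with the words. The rule decides membership of the primary analysis set for percent time with pH below 4, so two analysts could each follow the text and analyse different sets.

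The subjects affected have come back for a 24-hour catheter test after leaving. Section 10.0 warns that dropouts are often not a random sample and adds the recall visit to limit missing data. Discarding a completed final test because of the cut-off defeats that aim. A rule left unsettled may also end up being settled after the data have been seen.

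**Working it through.** **Inputs.** Study length is 9 weeks, or 63 days, with final testing on day 63 (Sections 2.1 and 6.0). The diet starts at the end of week 1 (Section 2.2), leaving 8 weeks, or 56 days. The verbal limit is 2 weeks early and the numeric limit is 0.8 (Section 10.0). The power inputs (Section 2.2) are SD 9.8, intraclass correlation 0.39, 40 completers per arm, 5 or 3 early leavers per arm, and a 4-d.f. test at two-sided 0.05.

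**Step 1: p for a subject leaving two weeks early.**

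| Clock | p | p ≥ 0.8? |
|---|---|---|
| 9-week study, weeks | 7/9 = 0.778 | no |
| 9-week study, days | 49/63 = 0.778 | no |
| From diet start, weeks | 6/8 = 0.75 | no |
| From diet start, days | 42/56 = 0.75 | no |

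A 10-week denominator would give 8/10 = 0.80, but the documents contain no such denominator.

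**Step 2: what 0.8 actually allows.** On the 9-week clock, 0.8 × 9 = 7.2 weeks (0.8 × 63 = day 50.4), so at most 9 − 7.2 = 1.8 weeks early. From diet start, 0.8 × 56 = 44.8 diet days, which is study day 7 + 44.8 = 51.8, so at most 63 − 51.8 = 11.2 days, or 1.6 weeks, early.

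**Step 3: share of the recall window excluded.** Assume exits spread evenly over days 49 to 63, a 14-day window. The documents give no exit distribution.

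- Days, 63-day clock: (50.4 − 49)/14 = 10%.
- Days, from diet start: (51.8 − 49)/14 = 20%.
- Completed weeks, 9-week study: everyone leaving on days 49 to 55 has p = 7/9, and from day 56 p = 8/9 = 0.889, so 7/14 = 50%.

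**Step 4: power.** The plan's table was reproduced first, by generalised least squares for the Section 10.0 model and a noncentral chi-square with 4 d.f., taking 9.8 as the within-subject SD and early leavers at t = 0.8.

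| Scenario | Plan, 5 leavers/arm | Recomputed | Plan, 3 leavers/arm | Recomputed |
|---|---|---|---|---|
| 3.7 in all four arms | 0.80 | 0.815 | 0.79 | 0.801 |
| 0, 4.5, 4.5, 4.5 | 0.89 | 0.895 | 0.88 | 0.885 |
| 0, 4, 4, 4 | 0.80 | 0.802 | 0.79 | 0.788 |
| 0, 0, 5, 5 | 0.85 | 0.859 | 0.83 | 0.847 |
| 0, 0, 0, 7 | 0.87 | 0.883 | 0.86 | 0.872 |

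All agree within 2 points. Reading 9.8 as the total SD gives 0.96 to 0.99, which does not match the table.

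Next, five leavers per arm were spread evenly over days 49 to 63, and power was compared with and without the p ≥ 0.8 cut, for 3.7 in all arms:

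- Days, 63-day clock: 0.8219 to 0.8188, a loss of 0.3 points.
- Completed weeks: 0.8174 to 0.8013, a loss of 1.6 points.

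Over all five scenarios, 3 or 5 leavers per arm, and either reading of the SD, the loss is at most 0.3 points (days) or 0.2 to 1.6 points (completed weeks). The spread-out exits are illustrative and are not the plan's own assumption.

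**Step 5: leaving date or test date.** Section 6.0 says "PPIs will be stopped for 1 week" before testing, and Section 2.1 keeps acid suppression in place "with the exception of the 7-day period prior to impedance and manometry testing". If such a stop preceded a leaver's final test, a subject leaving on day 49 and tested on day 56 would have 49/63 = 0.778 by leaving (out) and 56/63 = 0.889 by testing (in). The documents do not say how the stop applies to early leavers.

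**The case against.** **Rounding.** To one decimal, 7/9 is 0.8, and the power section uses the same 80%. Most likely one rule was meant and was written loosely. That explains the discrepancy but does not remove it. In a power calculation 80% is a harmless approximation; with a ≥ sign in an inclusion rule it is a hard boundary, and no rounding rule is given.

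**The definition of t.** Section 10.0 does set t equal to p, the proportion completed on leaving, so an operational definition exists, and Section 6.0 places the visit at drop-out. The day-49/day-56 case is therefore a hypothetical. What stands is that the label given to t points to the test while p points to leaving.

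**Subject counts.** A reader might apply the 10% or 50% to the 5 or 3 early leavers per arm in the power section and announce a number of subjects lost. The documents do not support that: those subjects are defined as having completed 80%, so they already pass the rule.

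**The recall request.** A reader might also take the missing-data text as a third statement of inclusion. It only requests a visit.

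**The start of the window.** Between weeks 7 and 9 could be read to include someone leaving during week 7, before day 49. The two-week verbal limit does not reach that far, so the end of week 7 is the reading that the two texts share.

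**Conclusion.** The contradiction holds on every clock that the documents offer. It rests on one division and needs no outside assumption: leaving two weeks early gives 0.778 or 0.75, and the cut-off is 0.8. The 10%, 20% and 50% shares rest on evenly spread exits, and the last also on counting whole weeks.

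A reader might infer that the trial is underpowered or that its result would be biased. Neither follows. The power loss is at most about 1.6 points under the illustrative exits. No bias has been shown, and Section 10.0 already plans analyses under dropout assumptions from missing completely at random to informative. This is a wrong threshold in the primary-analysis-set rule, which should be corrected before analysis. It is not a sample-size error.

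**What to change.** 1. In Section 10.0, replace the 0.8 cut-off with a rule in study weeks: besides completers, include every randomised subject who leaves at or after the end of study week 7 and returns for final pH testing. This gives the same set however p is counted, and agrees with the verbal rule and with Section 6.0 as read above.
2. Separately, define the clock for t. Say which pH test is t = 0 and whether the clock starts there, at study day 1, or at diet start at the end of week 1. Fixing it on 63 days by default would count the pre-diet week as exposure (0.778 against 0.75 at the end of week 7) in a model that scales the diet effect by t.
3. State whether t for an early leaver follows the leaving date or the test date.

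The cost is one sentence for the inclusion rule and one or two for t. No extra visits, data or subjects are needed.
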